We will measure HED with a question on how often the respondent drank 5 or more drinks on a single occasion (considering a 1-month period). The options were never, once, twice, 3 to 5 times, 6 to 9 times and 10 or more. We will convert this information into a continuous variable. We will convert the options 3-5 and 6-9 times to their arithmetic midpoint (4 and 7.5, respectively). We will convert the 10 or more option into the lower boundary (i.e., 10). This data is available for waves 0, 1, 4, 5 and 6.

We will measure the number of daily cigarettes smoked per day with a question on how many cigarettes has the participant smoked on average during the past week. We will convert this information into a continuous variable. This data is available for all waves.

Procedures

We collected the data using an online survey sent by email to all eligible participants. Data were collected from July 27 to August 13 (wave 0 and 1), August 15 to August 25 (wave 2), September 7 to September 22 (wave 3), October 5 to October 16 (wave 4), November 9 to November 20 (wave 5), December 9 to December 21 (wave 6) and April 5 to April 23 (wave 7). In all waves, we used an online survey tool (QuestionPro) which creates a database automatically. We did not allow participants to leave questions blank, but participants could stop answering at any moment. We used the following protocol to remind participants to answer the questionnaire: After sending the survey, we sent a reminder every three days: twice via email, then to those who had provided a mobile phone number, we sent the survey

two more times via text messaging. No incentive was provided in exchange for their participation in any of the study waves. The first round of data collection included questions regarding the period before the COVID-19 pandemic (wave 0) and during the pandemic (wave 1).

Sample size calculation

Prior to the beginning of the study, we calculated a sample size of 1046 participants to detect a small effect size (0.2), with a statistical power of 0.95, alpha of 0.05 and a factor of 2 to take into account the impact of attrition.

Ethical approval

The Scientific Ethics Committee from the Universidad de la Frontera and Universidad Católica del Norte approved the study in accordance with Law 20.120 (2006). We obtained electronic written consent from all participants.

Statistical analysis

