where Y_{ist} is the outcome for an individual s at time t and i is the region (Coquimbo or Araucanía), δ_{DD} is the coefficient of interest of a treatment intensity variable, X_{ist} is a vector of control variables (e.g. age, sex), β_i is a region fixed effect, and γ_t is a set of time fixed effects. The identifying assumption, in this case, relies on a common trend assumption that both treatment groups would develop equally over time under at least one of the treatments. It assumes effect homogeneity conditional on observables X_{ist} .

An alternative to adjustment by control variables would be to use propensity score matching (PSM). Recent analyses Daw and Hartfield (2018) suggest that using PSM could increase bias due to regression to the mean when treatment assignment occurs at the population level. In this context, the difference between treatment groups is stable and unmatched analysis is unbiased. Matching on the preperiod level introduces regression to the mean bias [38]. For this reason, we chose to adjust for control variables and not to use PSM.

There is an ongoing debate about DiD when groups of units receive treatment at different times or different treatment intensities.[39, 40] Researchers are concerned this fixed effect regression provides greater weights to treatments with similar before and after treatment periods and uses treated units as controls.[39] This is unlikely to affect our study, as it has only two treated groups and thus no variation in treatment timing. Nonetheless, we will use the Callaway-Sant'Anna method (CS method) in sensitivity analyses. The method was built to handle staggered treatment adoption designs.[40] To accommodate this, we will divide the analysis into two sections (t_0 versus t_1 , t_2 and t_3) and (t_0 versus t_5 and t_6).

The estimation will be done using linear mixed effects models. These models take into account the correlated nature of the data (repeated measures of the same individuals) and provide mathematically equivalent estimates than fixed effects linear regression. However, an additional advantage of linear mixed effects models is that they allow to vary the number of observations within each participant, handling missing data more efficiently than other analytical approaches [41].

Statistical Software

We will use R (current version 3.6.3) for all analyses. We will use the *lme4* function to run the DiD model and the *did* package for the Callaway-Sant'Anna method.

References

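### Does the 1,046-participant, 95%-power statement need reworking because it names no test and is tied to none of the planned analyses?

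*Combined protocol and SAP*

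**What the plan says.** The section Sample size calculation is a single sentence: "we calculated a sample size of 1046 participants to detect a small effect size (0.2), with a statistical power of 0.95, alpha of 0.05", together with "a factor of 2 to take into account the impact of attrition". It names no outcome, test or model.

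The Statistical analysis section plans two things. The main analysis is a seven-period, two-region DiD fitted by a linear mixed model, in which the DiD parameter "is the coefficient of interest of a treatment intensity variable" running from 5 (step 1) to 1 (step 5). The second is the Callaway-Sant'Anna method, labelled a sensitivity analysis. For it the plan states "To accommodate this, we will divide the analysis into two sections": t0 against t1 to t3, and t0 against t5 and t6.

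There are three primary outcomes. For heavy episodic drinking (HED), Outcomes says "This data is available for waves 0, 1, 4, 5 and 6", so its first Callaway-Sant'Anna section is t0 against t1 only. On recruitment, Procedures says "We collected the data using an online survey sent by email to all eligible participants". The same section explains that waves 0 and 1 came from one round of data collection, and it describes the fieldwork in the past tense.

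**The concern.** A power statement should let a reader repeat the calculation and see which analysis it supports. This one does neither. The 0.2 could be the lockdown contrast or the effect of one intensity step. The correlation between a person's repeated answers, which largely decides the precision of a DiD estimate, is absent.

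The planned analyses also differ in precision. The main model uses all seven waves and the reversal of exposure between regions. Each Callaway-Sant'Anna section uses only part of the data. A reader who carries the 95% over to those sections could take a non-significant section as contradicting the main result when it only reflects a wider interval. HED would be the most exposed outcome, because it was not collected at waves 2 and 3.

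**Working it through.** **1. The stated figure.** Inputs from Sample size calculation: effect 0.2, power 0.95, alpha 0.05, attrition factor 2.

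- Two-sample test, n per group = 2(z_alpha + z_beta)²/d². Two-sided: 2(1.960 + 1.645)²/0.04 = 649.7, so 650 per group, 1,300 in total and 2,600 after doubling. One-sided: 2(1.645 + 1.645)²/0.04 = 541.1, so 542 per group, 1,084 in total and 2,168 after doubling.
- Paired t-test: 327 two-sided (654 doubled) or 272 one-sided (544 doubled).

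None of these is 1,046. Some choices that the plan does not state come close. A two-period DiD with correlation 0.8 needs 8(1 − 0.8)(1.960 + 1.645)²/0.04 = 519.8, so 520, or 1,040 doubled, which is 0.6% below 1,046. A chi-square test with w = 0.2 and 6 df needs 522, or 1,044 doubled. The figure is therefore open to more than one explanation and is not demonstrably wrong.

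**2. Power of the main DiD.** Assumptions: N = 1,046/2 = 523 analysed, equal regional split, two-sided 0.05, effect 0.2 SD for lockdown coded 0/1, complete waves, equal correlation rho between waves, participants the only source of error. Then

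Var(effect) = 4(1 − rho)/(N × Szz),

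where Szz is the sum of squared deviations, over waves, of the between-region difference in exposure. The pattern comes from Statistical analysis: Coquimbo in lockdown at t1 to t3, no difference at t0 and t4, Araucanía in lockdown at t5 and t6.

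- Seven waves (0, 1, 1, 1, 0, −1, −1): Szz = 5 − 1/7 = 4.857. At rho = 0, SE = √(4/(523 × 4.857)) = 0.0397, and 0.2/0.0397 − 1.96 = 3.08, so power is 99.9%. Higher rho raises it.
- HED, five waves (0, 1, 0, −1, −1): Szz = 3 − 1/5 = 2.8. At rho = 0, SE = 0.0523 and power is 96.9%. At rho = 0.3 it is 99.5%.

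The main model meets the stated 95% over the whole range of rho from 0 to 0.7.

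**3. Power of the sensitivity sections.** The same formula applies, with Szz = 3 − 9/4 = 0.75 for t0 v t1–t3, 2 − 4/3 = 0.667 for t0 v t5–t6, and 1 − 1/2 = 0.5 for HED t0 v t1.

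| Section | N | rho 0.3 | rho 0.5 | rho 0.7 | rho for 95% |
|---|---|---|---|---|---|
| t0 v t1–t3 | 523 | 66% | 80% | 95% | 0.70 |
| t0 v t1–t3 | 1,046 | 92% | 98% | 99.9% | 0.40 |
| t0 v t5–t6 | 523 | 61% | 75% | 93% | 0.73 |
| t0 v t5–t6 | 1,046 | 88% | 96% | 99.8% | 0.46 |
| HED t0 v t1 | 523 | 49% | 63% | 84% | 0.80 |
| HED t0 v t1 | 1,046 | 78% | 90% | 99% | 0.60 |

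For HED t0 v t1 the larger N is the more natural one if 1,046 counts those recruited. Both answers come from one questionnaire, so no between-wave dropout separates them; only people who stopped part-way through the survey are lost. More generally, 523 is an assumption. Everyone eligible was invited, and the protocol does not give the number who responded.

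**The case for a change.** The strongest case for a change is about how results are read. With 523 analysed and rho = 0.5, the section standard errors (0.071 and 0.076; HED t0 v t1 0.087) are more than twice those of the corresponding main models (0.028; HED 0.037). A true effect of 0.2 SD would then miss significance in 20%, 25% and 37% of analyses of these three sections. The plan gives no rule for judging agreement, and one sentence would supply it.

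The first part stands: the sections are less precise. That is expected of a sensitivity analysis that sets data aside. The sample-size sentence does not extend its 95% to them, and nothing in the plan says that they will be judged by significance. Comparing estimates and confidence intervals is the ordinary way to read such an analysis, and the plan does not stand in its way.

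A second objection concerns the scale of the 0.2. If it covered all four intensity steps and the regions differed by two, the contrast would be 0.10 SD and main-model power 85% to 99.6% at rho 0.3 to 0.7. If they differed by one step, it would be 0.05 SD and 33% to 63%. The ambiguity is real, but both readings are assumed. The section Comparator defines the contrast as lockdown against no lockdown, which makes that the natural meaning of 0.2. Table S1 keeps a weekend lockdown at step 2, so a gap from step 1 to step 2 fits that contrast poorly. The figure and table that show each region's step were not in the text available for this check.

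A third objection is that shocks shared by everyone in a region at a given wave would lower power. That is true in principle. The documents give no size for such shocks, and inference from two regions is a separate question from the sample-size sentence.

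**Conclusion.** The sample-size sentence leaves out its inputs, and 1,046 cannot be verified from what it states. This is a reporting gap, not an error with consequences. On the natural reading (0.2 SD for lockdown versus none, 523 analysed, equal split, two-sided 5%, complete waves, participants the only source of error) the main DiD has at least 99.9% power, and at least 96.9% for HED. The claim of 95% is met where the plan can fairly be taken to make it.

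The sensitivity sections have less power: at rho = 0.5, 80% and 75% with 523 and 98% and 96% with 1,046; HED t0 v t1 63% and 90%. The plan promises no power for them.

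No change follows because none would gain anything. The data are collected, so recruitment cannot respond. A power table over assumed correlations would be overtaken by the confidence intervals from the data. Reading the sections by estimate and interval is what a sensible analyst would do under the plan as written. The conclusion depends on the lockdown-versus-none reading of 0.2 and on participants being the only source of error, neither of which the protocol states outright.

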Third, governments have adopted policies that directly influence alcohol and tobacco availability and affordability. Such policies include total ban of tobacco (South Africa)[11] or alcohol sales (e.g. South Africa, India, Thailand, Panama),[12-15] changes in opening hours (as in parts of Chile and Mexico) and even raised alcohol taxes in some States in India [16].

Lockdowns, especially those that include statutory restrictions for people's mobility, have likely the largest potential effect on alcohol and tobacco use. Previous studies reporting the effect of COVID-19 lockdowns on alcohol use have reported a mixed picture, with some studies reporting an increase in high-risk drinking (either volume or heavy episodic drinking),[17-21] volume of alcohol use [22] and frequency of alcohol use [23], while other

studies have reported reductions in alcohol use [24-26]. Mixed changes on tobacco use have also been reported, with a relatively equal proportion of respondents describing an increase or reduction in their use of tobacco [17, 20, 27-30]. Evidence comes primarily from countries in Europe, the United States, Australia, and New Zealand. One common limitation of these studies is that they compare a pre-pandemic with a pandemic period and are thus not able to disentangle the direct effects of the pandemic with those from lockdown and curfew policies.

In this study, we will advance prior knowledge by providing evidence from a country in Latin America, one of the worst-hit regions worldwide. Latin America accounts for 8.4% of the global population, but 20.3% of the total SARS-COV2 cases and 30.2% of the COVID-19 deaths to date [31]. In addition, we will exploit the variation in lockdown policies in two regions in Chile to disentangle the effects of the COVID-19 pandemic with those from a lockdown.

The aim of the study is to examine the effect of a regional lockdown on alcohol use in two university populations in the Araucanía and Coquimbo regions in Chile. We will use a difference-in-difference analysis to obtain causal estimates of these COVID-19 policies.

Methods

Study design

The study is a controlled before-and-after study of COVID-19 policies in two Chilean regions. We will report the results in accordance with the Strengthening the Reporting of Observational Studies in Epidemiology (STROBE) statement [32].

Participants

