The study population are university communities from two regions in Chile (Coquimbo, northern Chile, and Araucanía, southern Chile). These university communities include undergraduate and postgraduate students, full-time and part-time academics, leadership positions, administrative staff and service personnel. Eligibility criteria include (1) those with study rights either at the undergraduate and postgraduate levels by July 27, 2020; or (2) workers with a full-time or part-time contract with the University, including academics and assistant personnel, (3) with an email registered in the Human Resource Office of each university.

Intervention

We will examine the effect of lockdown in the context of the COVID-19 pandemic. During the study period, the Chilean Ministry of Health established a five-step process for social distancing measures. These ranged from full lockdown (step 1) to almost no restrictions (step 5). Even under full lockdown, citizens were able to obtain permits for essential activities (e.g., buying food or going to the doctor). These permits had a maximum of two per week and were obtained in a virtual station of the Chilean Police Force (Carabineros de Chile). Table S1 describes the five phases in detail. Table S2 describes the different types of permits people were allowed to use. It must be noted that, due to the COVID-19 pandemic, the Chilean government issued a night curfew with a total prohibition to leave home between 22.00 and 05.00 for the whole country from March 22, 2020, to date. Table 1 includes the specific policies implemented in both regions at the time of each data collection period.

Comparator

The comparator is the absence of lockdown at a given time. During most of the study period, the whole country had in place restrictions for public gatherings, school closures and advice for remote work. Both universities instructed remote work from March 16, 2020, which continued during the whole study period.

Covariates

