We will exploit the variation in lockdown policies in the two regions to measure the effect of lockdown on alcohol use. For this purpose, we will use a difference-in-difference (DiD) design to compare the effect of lockdown in multiple treatment periods. DiD is a quasi-experimental approach that allows using longitudinal data to obtain causal effects in the absence of randomization [33]. DiD is a well-established method in public health research and was first used by John Snow in his seminal study on the transmission of cholera in 1855 [34].

The canonical DiD consists of two time periods and two groups. One computes the difference in the mean outcomes of the treatment and control group after the treatment and subtract the difference that existed before treatment had any effect [35].

$$\delta_{DD} = (\underline{Y}_{posttreat} - \underline{Y}_{pretreat}) - (\underline{Y}_{postcontrol} - \underline{Y}_{precontrol})$$

The key identifying assumption is that, in the absence of treatment, the average outcomes would have followed parallel paths over time [33].

As depicted in Figure 1, our case is more complex, as there are multiple time periods (seven in total) and two groups that are both treated and not-treated in different time periods. For τ periods and a particular time period denoted by t where $t=1,..., \tau$, t_0 represents the baseline measurement captured retrospectively at t_1 . In time periods t_1 , t_2 and t_3 , the Coquimbo group

is exposed to lockdown while the Araucanía group is exposed to less restrictive social distancing policies. At t_4 both groups are exposed to step 2 social distancing policies and at t_5 and t_6 ; this situation reverses, and Araucanía is exposed to lockdown and Coquimbo moves to less restrictive social policies. Treatment intensity *D* has values ranging from 5 (step 1) to 1 (step 5) (see Table S2 for details).

[figure not shown]

Figure 1. Social distancing policies in Coquimbo and Araucanía for the study period

In this setting, we will use a generalized difference-in-difference that allows for multiple treatment periods and several treatment intensities [36, 37]. The regression of a DiD model can be expressed in more general terms as

$$(1) Y_{ist} = \alpha + \delta_{DD} TREAT_{st} + \theta X_{ist} + \beta_i + \gamma_t + e_{ist}$$

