Step 2	Yes	Yes, only Saturdays, Sundays and bank holidays	Remote education for preschool, elementary and higher schools	Open at 25% of their maximum capacity, maximum time two hours, only in open spaces	Sports activities for maximum 10 people in open spaces. Gyms closed	Public events allowed for a maximum of 10 people in a closed space and 20 people in an open space.	Closed	Customer service restricted to no more than 1 person per 10 square meters	Passenger cruises forbidden. All buses must have a list of passengers for travelling times longer than 2 hours. Forbids travel to second residence. 1	Allowed	Lockdown for residents in elderly care. Closure of day centers for older adults and meetings of "Clubes de Adultos Mayores"

Step 3	Yes	No	Allowed after permission from Regional Secretary of Education	Open at 25% of their maximum capacity, maximum time two hours, only in open spaces	Sports activities for maximum 25 people in open spaces and 5 people in closed spaces, including gyms	"Oficios, ritos, seminarios and ceremonias" allowed for a maximum of 25 people in a closed space and 50 people in an open space.	Closed	Customer service restricted to no more than 1 person per 10 square meters	Allows travel to second place of residence	Allowed	Lockdown for residents in elderly care. Closure of day centers for older adults and meetings of "Clubes de Adultos Mayores"
Step 4	Yes	No	Allowed after permission from Regional Secretary of Education	Open at 50% of their maximum capacity	Sports activities for maximum 50 people in open spaces and 10 people in closed spaces, including gyms	"Oficios, ritos, seminarios and ceremonias" allowed for a maximum of 50 people in a closed space and 100 people in an open space.			Allows travel to second place of residence	Allowed	Lockdown for residents in elderly care. Closure of day centers for older adults and meetings of "Clubes de Adultos Mayores"
Step 5	Yes	No	Allowed after permission from Regional Secretary of Education	Open at 75% of maximum capacity	Sports activities for maximum 100 people in open spaces and 20 people in closed spaces, including gyms	"Oficios, ritos, seminarios and ceremonias" allowed for a maximum of 100 people in a closed space and 200 people in an open space.	Open at 75% of maximum capacity		Allows travel to second place of residence	Allowed	Visits to elderly care centers are allowed. Day centers for older adults open

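### The main model estimates an effect per step of restriction, but the aim and comparator call for lockdown versus no lockdown, and no conversion is given

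*Combined protocol and SAP*

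**What the plan says.** The end of the Background section gives the question: "The aim of the study is to examine the effect of a regional lockdown on alcohol use in two university populations". The Comparator section matches it: "The comparator is the absence of lockdown at a given time". Both describe a two-state contrast.

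The Intervention section describes a five-step scheme: "These ranged from full lockdown (step 1) to almost no restrictions (step 5"). The Statistical analysis section turns this into a score: treatment intensity D "has values ranging from 5 (step 1) to 1 (step 5"). Equation (1) has one term for treatment, and the text below it says that its coefficient "is the coefficient of interest of a treatment intensity variable".

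On exposure, the Statistical analysis section says that at t_1 to t_3 the Coquimbo group "is exposed to lockdown while the Araucanía group is exposed to less restrictive social distancing policies". Both regions are at step 2 at t_4, and the roles reverse at t_5 and t_6. The text does not number the steps of the less restricted region. They belong to Table 1 and Figure 1, which were not available for this review.

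Table S1 gives lockdown at step 1 without limitation, at step 2 as "Yes, only Saturdays, Sundays and bank holidays", and none at steps 3 to 5.

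**The concern.** One coefficient on one numeric score is a change in outcome per step. It treats a move from step 5 to step 4 as worth the same as a move from step 2 to step 1. The plan neither justifies that spacing nor says how many steps make up the lockdown effect it wants to report. Followed as written, it gives a number that does not directly answer the stated question.

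The spacing matters because the lockdown component in Table S1 changes only between steps 1, 2 and 3. The Background section itself expects statutory limits on mobility to have the largest potential effect. If that is so, the size of the per-step coefficient depends on which step the comparison region happened to be in. A reader could take the coefficient for the lockdown effect and misjudge its size.

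**Working it through.** The plan gives no figure for this contrast to reproduce. Its design effect size of 0.2 carries no unit or contrast. The check asks what the planned coefficient returns under two opposite assumptions about the true effect.

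**Inputs.** D = 6 − step (Statistical analysis). Coquimbo is at step 1 at t_1 to t_3, both regions are at step 2 at t_4, and Araucanía is at step 1 at t_5 and t_6 (same section). Assumed, because not visible: Araucanía at step a throughout t_1 to t_3 and Coquimbo at step c throughout t_5 and t_6, each of a and c being 2, 3 or 4. The two regions share the same value at t_0, so its coding drops out. Region-by-wave means are taken as noise-free and equally weighted.

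**Reduction.** With two regions and region and time effects, the coefficient in equation (1) is the slope, with intercept, of the between-region outcome difference on the between-region exposure difference over the seven waves. Put g = a − 1 and h = c − 1. The differences (Coquimbo minus Araucanía) for t_0 to t_6 are:

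- score D: 0, g, g, g, 0, −h, −h
- step-1 indicator: 0, 1, 1, 1, 0, −1, −1

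Hence:

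- Sxy = (3g + 2h) − (3g − 2h)/7
- Sxx for the score = 3g² + 2h² − (3g − 2h)²/7
- Sxx for the indicator = 5 − 1/7 = 34/7

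**Case A: only step 1 has an effect, L.** Score coefficient = L × Sxy/Sxx(score). The indicator returns L.

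**Case B: the effect is linear, b per step.** The score returns b. Indicator coefficient = b × Sxy/(34/7).

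Example, a = 3 and c = 2 (g = 2, h = 1): Sxy = 8 − 4/7 = 52/7 and Sxx(score) = 14 − 16/7 = 82/7. Case A gives 52/82 = 0.63 L; Case B gives 52/34 = 1.53 b.

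| Araucanía a | Coquimbo c | Case A: score, × L | Case B: indicator, × b |
|---|---|---|---|
| 2 | 2 | 1.00 | 1.00 |
| 2 | 3 | 0.66 | 1.47 |
| 2 | 4 | 0.48 | 1.94 |
| 3 | 2 | 0.63 | 1.53 |
| 3 | 3 | 0.50 | 2.00 |
| 3 | 4 | 0.40 | 2.47 |
| 4 | 2 | 0.45 | 2.06 |
| 4 | 3 | 0.39 | 2.53 |
| 4 | 4 | 0.33 | 3.00 |

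A comparator at step 5 throughout would give 0.25 L in Case A. For illustration, if L were 0.2 SD, the score would report 0.20, 0.10 or 0.067 SD with the comparator at step 2, 3 or 4 throughout.

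**Equal gaps.** If g = h = k, then D equals a wave-specific constant plus k times the indicator. The time effects absorb the constant, so the fit and the test statistic are identical and the coefficient is divided by k. Only the size and meaning of the estimate change.

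**Heavy episodic drinking.** This outcome has waves 0, 1, 4, 5 and 6 only. With a = 3 and c = 2, Sxy = 4 and Sxx(score) = 6, so Case A gives 0.67 L against 0.63 L on all waves. With unequal gaps, the score therefore means something slightly different across the primary outcomes.

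**Step 2.** Suppose step 2 carries 2/7 of L (assumption: two weekend days in seven). A step-1 indicator that classes step 2 as no lockdown then returns 0.71 to 0.87 L when either comparator is at step 2, and 1.00 L otherwise. At a = c = 2: 1 − 2/7 = 0.71.

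**The case against.** The strongest reply is that a graded exposure is a deliberate and sensible choice. Table S1 has bars and restaurants closed except for take-away at step 1, at 25% capacity at steps 2 and 3, 50% at step 4 and 75% at step 5. Gathering limits also rise step by step. These could well drive drinking. If the effect is linear in step, the score is stable and the step-1 indicator is the quantity that moves with the comparator, as Case B shows. This stands. A reader might infer that the score is biased and the indicator correct; the documents support neither, because they do not say which component of the steps drives the outcomes.

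A second reply is that the coding is inferred: no sentence sets TREAT equal to D or says that it enters linearly. That is true, but the definition of D, the single coefficient and the description of it as belonging to an intensity variable leave no other definition in the text. If categories were intended, the plan needs to say so.

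Third, the Callaway-Sant'Anna analysis splits the waves into t_0 against t_1 to t_3 and t_0 against t_5 and t_6. It may therefore yield a lockdown contrast. The plan does not state its exposure coding, and it is a sensitivity analysis, so it does not supply the headline estimate.

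A reader might also infer that the hypothesis tests are invalid. They are not on this ground: with equal gaps the p-value is the same, and whether the gaps differ cannot be judged from the text available.

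**Conclusion.** The mismatch stands. The stated question is lockdown versus its absence, the main coefficient is per step, and no rule links the two. Even if the effect is truly linear, the lockdown effect is the coefficient multiplied by the step gap, and the plan does not provide for that calculation.

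The size is conditional on comparator steps 2 to 4, equally weighted waves and the assumed shape of the effect. The per-step coefficient is 0.33 to 1.00 times the lockdown effect if only step 1 matters. If the effect is linear in step, it is stable at 1.00 per step and the step-1 contrast is 1 to 3 times it. No single figure for the discrepancy can be given without each region's step at each wave. The matter is one of estimand and interpretation, and it is cheap to put right with the data already collected.

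**What to change.** - Make the lockdown contrast that matches the Comparator section the headline estimate, using a step-1 indicator.
- Give step 2 its own category where it can be estimated. With wave effects in the model and both regions at step 2 at t_4, that requires a comparator region at step 2 in some, but not all, of the contrasted waves. If every comparator wave is at step 2, the two indicators are collinear. If step 2 cannot be estimated, state how it is classed and describe the contrast accordingly.
- Report the 5-to-1 score alongside as a dose-response analysis, with its coefficient labelled per step.
- State each region's step at each wave next to the estimates. Point the definition of D to Table S1; the text now cites Table S2, which lists mobility permits.
- Date and justify the change. Version 1.0 is dated October 5, 2021 and describes data collection as already done, so the change should be visible as made after that.

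The cost is one recoded variable, one further model run per outcome and a short amendment, with no new data. The real downside is that the lockdown contrast ignores differences among steps 3 to 5 and averages over whatever step the comparator region was in. That is why the score should stay beside it.

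### Lockdown timing does vary between the two regions, so the pooled coefficient and the second Callaway-Sant'Anna section rest on a no-carry-over assumption that the plan never states explicitly

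*Combined protocol and SAP*

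**What the plan says.** All of this is in the protocol's Statistical analysis section unless noted.

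- **Schedule.** At t_1, t_2 and t_3 Coquimbo "is exposed to lockdown while the Araucanía group is exposed to less restrictive social distancing policies". At t_4 both regions are at step 2. At t_5 and t_6 "this situation reverses, and Araucanía is exposed to lockdown and Coquimbo moves to less restrictive social policies".
- **Model.** Equation (1) has region effects, period effects, covariates and the current treatment intensity TREAT. It has no term for past lockdown. The Comparator section defines the contrast in the same current-status way: "The comparator is the absence of lockdown at a given time".
- **Stated assumptions.** The plan relies on "a common trend assumption that both treatment groups would develop equally over time under at least one of the treatments", and adds: "It assumes effect homogeneity conditional on observables".
- **The concern and its dismissal.** The plan notes a debate over regressions of this kind, including the criticism that such a model "uses treated units as controls". It then answers: "This is unlikely to affect our study, as it has only two treated groups and thus no variation in treatment timing".
- **Sensitivity analysis.** Callaway-Sant'Anna is still planned, in two sections. Section 1 is t_0 against t_1, t_2 and t_3. Section 2 is "t_0 versus t_5 and t_6".

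**The concern.** Having two groups does not imply common timing, and here the timing is opposite. When Araucanía is locked down at t_5 and t_6, the only available comparator is Coquimbo, which was locked down at t_1 to t_3. If drinking or smoking in Coquimbo has not returned to what it would have been without that lockdown, the comparator is displaced, and equation (1) has no term to absorb the displacement. Section 2 of the sensitivity analysis uses the same comparator, so it does not escape the problem.

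The study aims at causal estimates. A lasting effect of the first lockdown would shrink the pooled estimate, and a rebound would inflate it. The plan also does not say how a difference between sections 1 and 2 would be read.

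**Working it through.** The plan gives no figure on this point, so there is none to reproduce. The calculation below shows sensitivity to an assumed carry-over.

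**Inputs from the documents.** Seven periods, t_0 to t_6, with the schedule above. Under Outcomes, heavy episodic drinking (HED) is available at waves 0, 1, 4, 5 and 6 only.

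**Assumptions.** True lockdown effect 1 in both episodes; equal gaps in intensity between regions in the two episodes; balanced panel; parallel trends. Let c be the share of Coquimbo's effect still present at t_4 to t_6. The documents give no value for c; a negative c means rebound.

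**Step 1: weights.** With two regions, equation (1) reduces to regressing the Coquimbo-minus-Araucanía outcome gap on the treatment contrast d.

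- Seven waves: d = (0, 1, 1, 1, 0, -1, -1), mean 1/7, sum of squares 5 - 1/7 = 34/7. The weights on the gaps are (7d - 1)/34 = (-1, 6, 6, 6, -1, -8, -8)/34.
- HED: d = (0, 1, 0, -1, -1), mean -1/5, sum of squares 3 - 1/5 = 14/5. The weights are (5d + 1)/14 = (1, 6, 1, -4, -4)/14.

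**Step 2: stable carry-over.** This adds c to the gap at t_4, t_5 and t_6.

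- Pooled, seven waves: 1 + c(-1 - 8 - 8)/34 = 1 - c/2.
- Pooled, HED: 1 + c(1 - 4 - 4)/14 = 1 - c/2.
- Section 2 (gap at t_0 minus mean gap at t_5 and t_6): 1 - c.
- Section 1 (mean gap at t_1 to t_3 minus gap at t_0): 1, whatever c is. For HED it rests on t_1 alone.

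| c | Pooled | Section 2 |
|---|---|---|
| -0.5 | 1.25 | 1.50 |
| 0 | 1 | 1 |
| 0.5 | 0.75 | 0.50 |
| 1 | 0.50 | 0 |

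Coding intensity from 1 to 5 gives the same pooled multipliers, whether the less restrictive level is taken as 2, 3 or 4.

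**Step 3: fading carry-over of 0.5, 0.25, 0.125 at t_4, t_5, t_6.**

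- Pooled: 1 - (0.5 + 8 × 0.25 + 8 × 0.125)/34 = 1 - 3.5/34 = 0.90.
- HED: 1 + (0.5 - 4 × 0.25 - 4 × 0.125)/14 = 1 - 1/14 = 0.93.
- Section 2: 1 - (0.25 + 0.125)/2 = 0.81.

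**Step 4: what else separates the sections.** Suppose no carry-over, but the regional gap drifts by 0.1 per wave. Section 1 becomes 1 + (0.1 + 0.2 + 0.3)/3 = 1.20, and section 2 becomes 1 - (0.5 + 0.6)/2 = 0.45. A difference is therefore not specific to carry-over.

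**Step 5: precision of the comparison, with independent equal-variance errors in the gaps.** Section 1 minus section 2 has variance 1/3 + 1/2 + 4 = 4.83, SE 2.198. The pooled SE is √(7/34) = 0.4537, so the ratio is 4.85. For HED it is √(1 + 1/2 + 4)/√(5/14) = 2.345/0.5976 = 3.92.

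**Step 6: two possible corrections under the fading case of step 3.** Section 2 based at t_4 gives 0.5 + (0.75 + 0.875)/2 = 1.31. Adding a Coquimbo post-lockdown indicator at t_4 to t_6 leaves a sum of squares of 3/4 + 2/3 = 17/12 for d. The bias is then (2/3 × 0.5 - 1/3 × 0.25 - 1/3 × 0.125)/(17/12) = 0.147, so the estimate is 1.15. For HED the sum of squares is 1/2 + 2/3 = 7/6, and the estimate is 1.18.

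**The case against.** The strongest reply is that the assumption is already there. If both regions must follow common trends under the less restrictive regime, and the comparator is defined by current status, then a displaced post-lockdown Coquimbo would violate the stated assumption. That reading is available, and it makes the gap one of explicitness. But the text does not spell it out, and it gives an incorrect reason for thinking the issue does not arise.

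A second reply is that the plan recognises the two episodes and splits the Callaway-Sant'Anna analysis accordingly. This also stands in part. Under stable carry-over, section 1 minus section 2 equals 1 - (1 - c) = c, so the planned pair already contains a contrast that responds to carry-over. It is imprecise, is confounded with drift, and comes with no rule for reading it.

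A third reply is that the SE ratios assume independent errors, although waves 0 and 1 come from one survey round. This is fair. With an assumed t_0/t_1 error correlation of 0.6, the ratio falls from 4.85 to about 4.49, and for HED from 3.92 to about 2.80. The comparison remains imprecise.

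A reader might also infer that section 1 is contaminated by an earlier lockdown in Araucanía. The documents do not support that. Table 1 and Figure 1 cannot be read here, and nothing in the readable text indicates such a lockdown.

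**Conclusion.** The stated ground for setting the concern aside is wrong as written: the schedule in the same section shows opposite timing. The pooled coefficient and section 2 need the first lockdown to leave no effect at t_4 to t_6. That is at most implicit in the plan. This should be fixed.

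A reader might go further and infer that the primary estimate is biased or that the primary model must be replaced. The documents support neither. They contain no evidence of carry-over, and at c = 0 with parallel trends the pooled estimate is correct by this route. The multipliers in the working depend on an assumed c, equal gaps between regions and a balanced panel; they show sensitivity, not demonstrated bias. The contradiction between the sentence and the schedule depends on none of these assumptions. Section 1 is untouched by carry-over from Coquimbo's t_1 to t_3 lockdown.

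**What to change.** 1. Replace the sentence on timing. Say that lockdown timing differs between the regions, and that the pooled coefficient and section 2 assume no effect of Coquimbo's lockdown remaining at t_4 to t_6.
2. State in advance that sections 1 and 2 are each reported alongside the pooled estimate. If they differ, say that carry-over, regional drift or a real difference between the two episodes may be the cause, and do not then read the pooled coefficient as a single lockdown effect. Say also that finding no detectable difference does not show absence of carry-over.
3. Optional and exploratory only: a Coquimbo post-lockdown indicator in equation (1), or t_4 as a second base for section 2. Each removes only stable carry-over. In the fading case both land further from 1 than the planned estimates do: 1.15 against 0.90 for the pooled fit, and 1.31 against 0.81 for section 2. They should not replace the planned analyses.

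Items 1 and 2 need only changes of wording and no new data. The price is a more cautious conclusion, resting partly on a section comparison whose SE is several times the pooled SE.
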